9.3.1 Participant Adherence- Acupressure

Participants will be asked to log time spent using the AcuWand on a daily basis and record any reasons for missed sessions. The Acuwand device also records the time a participant spends using the device. A check in call will be made by the study team 48 hours after starting the treatment to address any patient questions or concerns. An additional call will be made two weeks after start of treatment to assess adherence. Text messages remind participants to charge the AcuWand device will be sent at week 4 and 6 of treatment.

9.3.2 Standardizing Assessment and Intervention

Fidelity of the acupressure intervention in study staff, who are teaching participants acupressure, i.e., acupressure educators will be assessed by study investigator [name] every six months. Educators will be trained using the BACPAC Acupressure Therapist Treatment Manual (see supporting documents).

9.4 Duloxetine

All study activities for this arm will take place at the Back & Pain Center, Department of Anesthesiology, at the Burlington Building in Ann Arbor or on a HIPAA compliant virtual platform like Zoom. Participants randomized

Figure 7 Sample MeTime Acupressure App

[figure not shown]

Figure 8 Location of Acupressure Points

to the duloxetine arm will review the dosing schedule for the medication and safety information for the medication at the pre-intervention visit (T2 for Treatment 1 or T3 for Treatment 2) with the study coordinator. At the baseline visits a physical exam was performed by a physician and drug contraindications will be reviewed as an additional precautionary measure.

Participants will then be given 105 pills of 30mg duloxetine with an 8-week dose escalation schedule and an additional 11 pills for those who would like to taper. Participants will be asked to start taking the medication from home, 7 days after the pre-intervention visit (T2/T3 visit). In the event of a shutdown due to COVID, participants may be mailed the study medications by the research pharmacy.

The first day of the medication will be day 1 and subjects will be scheduled for a phone visit with the study team at day 7 and day 42 (or the next business day if this falls on a weekend). A check in call will be made by the study team 48 hours after starting the treatment to address any patient questions or concerns. For days 1-7, patients will take 30mg of duloxetine once a day, in the morning. Starting day 8, participants tolerating the medication will be escalated to 60mg once a day. They will also have the option of staying at 30mg, once a day or stopping the medication (see Figure 9 below).

Participants will be scheduled for a phone visit with the study team at the end of week 1 to discuss dose escalation and at the end of week 6 to discuss dose taper. At the end of the 8-week intervention period, participants will have the option to continue the medication commercially (non-study medication) under the care of their physician or taper off the medication. During the entire 8-week intervention, patients will be asked to keep a daily log of medication dosage, any missed doses, and any side-effects they may have experienced.

9.4.1 Dose Escalation

At the day 7 call, the study staff will document any adverse events and safety concerns the patients may have. Willing subjects will be asked to increase the dose to 60mg, once a day, in the mornings. Participants will also have the option of staying at a dose of 30mg per day or stopping the medication entirely. If day 7 is on a weekend, the call will be scheduled for the next business day.

9.4.2 Dose Taper

At the day 42 call, the study team will document any adverse events and safety concerns. Participants who are tolerating duloxetine and want to continue therapy using commercial medication, will be asked to obtain a prescription for duloxetine from their primary care physician, or other provider. The study team can provide a letter with drug information. If at this time the patient is not interested in continuing duloxetine, the taper schedule will be explained (see Figure 9 below).

- A patient at the max dosage of 60mg will be asked to tapered down starting day 56 to 30mg for 7 days and then 30mg every other day for another 7 days, before stopping the medication completely. These additional 11 pills will be provided to the patient at the post-intervention visit. If day 42 is on a weekend, the call will be scheduled for the next business day.
- A patient on 30mg, will be asked to start tapering on day 56 by taking 30mg every other day for another 7 days, before stopping the medication completely.

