9.4.3 Duloxetine Post-Intervention Visit

When patients arrive for their post-intervention visit, the study team will document any adverse events, and/or safety concerns the participants may have. A daily log of medication dosage will also be collected from the patient at this point. Unused pills will be counted, documented and will be returned to the research pharmacy for accountability. Any additional pills for tapering will be provided for participants who want to taper.

Figure 6: Schedule of events for Duloxetine arm

[figure not shown]

Figure 9 Schedule of Events for Duloxetine Arm

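### Duloxetine taper: the Protocol gives two dispensing times for the 11 taper pills and a day-56 start that does not match the supply, so a late T3 can leave an adherent 60 mg participant without drug

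*Protocol*

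**What the plan says.** Protocol 9.4 describes the pre-intervention visit (T2 for Treatment 1, T3 for Treatment 2) and continues: "Participants will then be given 105 pills of 30mg duloxetine with an 8-week dose escalation schedule and an additional 11 pills", the 11 being for those who wish to taper. Dosing starts 7 days after that visit, and the first dose is day 1. The dose is 30 mg on days 1 to 7 and 60 mg from day 8 if tolerated, with the option to stay at 30 mg or stop. On what follows, 9.4 says: "At the end of the 8-week intervention period, participants will have the option to continue the medication commercially", or to taper off.

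Protocol 9.4.2 has the taper explained at the day-42 call to those who will not continue. A participant at 60 mg "will be asked to tapered down starting day 56 to 30mg for 7 days", and then takes 30 mg on alternate days for 7 more. On supply it says: "These additional 11 pills will be provided to the patient at the post-intervention visit". A participant at 30 mg "will be asked to start tapering on day 56 by taking 30mg every other day for another 7 days".

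Protocol 9.4.3, on the post-intervention visit, has unused pills counted and returned, and adds: "Any additional pills for tapering will be provided for participants who want to taper".

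Protocol 12.1 and SAP Table 1 put T2, T3 and T4 in weeks 6, 15 and 24. SAP 5.6 allows ±2 weeks around each. Protocol 14 schedules a visit immediately before and after each intervention period and lets these visits be virtual. Figure 9, this arm's schedule of events, is not shown in the text reviewed.

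**The concern.** Staff cannot follow both dispensing instructions. Under 9.4 the participant has the taper pills from the start. Under 9.4.2 they come only at the post-intervention visit. If 9.4.2 is followed and that visit is late, the main supply runs out first and the participant stops abruptly, which is what a taper is meant to avoid. A virtual visit makes handing pills over harder, since the Protocol mentions mailing only for a COVID shutdown or lockdown (9.4, 9.4.4).

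The start day is a second, smaller mismatch. Day 56 puts the first reduced dose about a day before the visit at which the primary endpoint is read, and it does not agree with the number of pills supplied.

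**Working it through.** **Reproducing the supply.**
- Main supply: 7 × 1 + 49 × 2 = 105, which is 30 mg for 7 days and then 60 mg on days 8 to 56 inclusive.
- Taper at 60 mg: 7 daily pills + 4 alternate-day pills = 11.
- Both stated figures reproduce. Total: 105 + 11 = 116.

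**Fit to the taper start.**
- Start on day 56: full dose through day 55 uses 7 + 48 × 2 = 103. Need 103 + 11 = 114, leaving 2 over. The last dose is on day 69.
- Start on day 57: full dose through day 56 uses 105. Need 105 + 11 = 116, leaving 0 over. The last dose is on day 70.

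The supply fits day 57 exactly. The written start is day 56.

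**Where T3 falls on the drug calendar.** T3 drug day = (days from T2 to T3) − 7 + 1.
- Same weekday in weeks 6 and 15: (15 − 6) × 7 − 7 + 1 = 57.
- From the week labels alone (week 6 = study days 36 to 42, week 15 = days 99 to 105): minimum 99 − 49 + 1 = 51, maximum 105 − 43 + 1 = 63.
- Late edge of the window, with T2 at its nominal date: 57 + 14 = 71.
- T4 when duloxetine is Treatment 2: (24 − 15) × 7 − 7 + 1 = 57, the same timing.

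**Gap at 60 mg if taper pills come only at T3, full adherence.**
- Stepped down on day 56 as written: 105 − 103 = 2 pills remain and cover days 56 and 57. Days without drug = T3 day − 58.
- Full dose through day 56: nothing remains for day 57. Days without drug = T3 day − 57.

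| T3 on drug day | Stepped down on day 56 | Full dose through day 56 |
|---|---|---|
| 57 (nominal) | 0 | 0 |
| 58 | 0 | 1 |
| 59 | 1 | 2 |
| 63 | 5 | 6 |
| 71 (window edge) | 13 | 14 |

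These are calendar days without drug. At the longer gaps some of them would have been off days in the alternate-day phase.

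**At 30 mg.** After day 55, 105 − 55 = 50 pills remain and the alternate-day taper needs 4. There is no gap.

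**If 9.4 is followed instead.** All 116 pills are in hand from the start, so a late visit by itself creates no gap.

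**The case against.** The best defence is that the intended order is clear and only a day number is off. The 11 pills are the whole 60 mg taper, so issuing them at the post-intervention visit implies visit first, taper second. The 105 pills run through day 56, and Protocol 14 plans T3 immediately after treatment. Figure 9 may show this order. The sentence in 9.4 could be a summary of total supply. A late T3 departs from the plan, and the gap also needs full adherence at 60 mg, a choice to taper, and pills issued only at T3.

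Most of this stands, and it keeps the point small. It does not remove it. Section 9.4 never says that it is a summary, and it follows directly on the pre-intervention visit. Whatever Figure 9 shows, the sentences in 9.4 and 9.4.2 would still disagree. SAP 5.6 allows the late visit.

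A reader might go further and infer that the primary endpoint is biased by the taper. The documents do not support that. At nominal timing T3 follows one or two reduced doses. Neither the share who taper nor the effect of a reduced dose on Pain Interference is given. Any shift would fall mainly on the duloxetine main effect and not on the treatment-by-phenotype interactions tested in SAP 9.1.1. The primary analysis is by assigned treatment (SAP 7.2.1), so values read after step-down belong in it.

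A reader might also want T3 moved earlier for taperers, or a sensitivity analysis that excludes values after step-down. Both would treat participants differently according to a choice made after randomisation, plausibly related to response or tolerability, and could add the kind of bias they are meant to remove.

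**Conclusion.** The point holds as a minor drafting conflict with one practical consequence. Protocol 9.4 and 9.4.2 contradict each other on when the taper pills are dispensed. The contradiction with 9.4.3 is softer, because that section gives no number and agrees with 9.4.2 only by its placement. The day-56 start is one day off the supply and looks like a slip for day 57.

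Followed literally, 9.4.2 causes no gap at nominal T3. From about day 58 or 59, depending on whether the participant steps down on day 56 or stays at full dose through it, there is a gap of at least one day, reaching 13 or 14 days at the window edge. This applies to fully adherent 60 mg participants who taper, at T3 or at T4 when duloxetine is second.

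The day counts assume dosing starts exactly 7 days after the pre-intervention visit. Day 57 assumes matching weekdays, and day 71 assumes that visit was on its nominal date. How many participants would be affected cannot be derived from the documents, nor can any effect on the T3 endpoint.

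**What to change.** Align Protocol 9.4, 9.4.2 and 9.4.3, for the duloxetine arm only:

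1. The 11 taper pills are dispensed with the main supply at the pre-intervention visit, as 9.4 already says. This also works when the post-intervention visit is virtual.
2. Taper pills still in use are kept by the participant when unused pills are returned at the post-intervention visit.
3. The taper starts on day 57, matching the 105-pill supply. Figure 9 should be checked against this.

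The cost is a few sentences. Participants who do not taper return 11 unused pills, so the returned-pill count used for compliance in SAP 8.5 has to be read against 116 dispensed. The last 60 mg taper dose moves from day 69 to day 70, adding at most one day to any overlap with Treatment 2. No visit, pill, assessment time or analysis is added or changed.

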9.4.3 Duloxetine Post-Intervention Visit

When patients arrive for their post-intervention visit, the study team will document any adverse events, and/or safety concerns the participants may have. A daily log of medication dosage will also be collected from the patient at this point. Unused pills will be counted, documented and will be returned to the research pharmacy for accountability. Any additional pills for tapering will be provided for participants who want to taper.

Figure 6: Schedule of events for Duloxetine arm

[figure not shown]

Figure 9 Schedule of Events for Duloxetine Arm

9.4.4 Medication Procurement and Storage

Medications will be procured from the research pharmacy on a weekly basis. Duloxetine will be stored in the research room's double locked cabinet. Temperature in the room must be managed between 20 -25°C (68-77°F); excursions permitted to 15-30°C (59-86°F) – per package insert. A log of maximum/minimum readings will be entered into a log while the drug is in research storage. Medications may also be mailed to patient directly, in the event of a lockdown due to COVID.

9.4.5 Medication Accountability

All study medication bottles will be collected/returned from the participant to the study team. When a bottle is returned, a study team member will count how many capsules or left and record the number on the bottle, date and initials. All medication bottles will be returned to the Research Pharmacy for drug accountability. The Research Pharmacy will be asked to sign off on the accountability log showing the bottle is returned. The Research Pharmacy will dispose of medication and bottles.

10 Deep Phenotyping Visits

A subset of study participants (n=160) be offered optional deep phenotyping. These participants will have a separate assessment appointment with study personnel at the CPFRC. There will be two visits that take place after T2-before Treatment 1 and after T3-before Treatment 2. At the deep phenotyping study visit, participants will undergo QST, Structural and functional brain neuroimaging, inflammatory markers assessment and the assessment autonomic functioning.

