6.8 Actigraphy and Ecological Momentary Assessment (EMA)

After completing the screening/baseline activities, participants will receive instruction on the use of the PRO-Diary monitor, which the participant will wear during 5 separate 7-day “home monitoring” periods, at baseline (sent home with watch following baseline visit) and T2-T5 to assess physical activity (objectively measured via accelerometry), and ecological momentary assessment (EMA) of mental and physical symptoms. EMA will be collected during Weeks 1, 6, 15, 24 and 36).

To measure real-time physical activity and collect ecological momentary assessment data, we will utilize the PRO-Diary (Figure 5 <http://www.camntech.com/products/pro-diary/pro-diary-overview>), a wrist-worn accelerometer with a touch-screen user-interface. The PRO-Diary collects physical activity data (via a triaxial MEMS accelerometer) as ‘activity counts’ during regular epochs during the home monitoring period and stores time-stamped self-report data until the participant returns the watch to the lab, where the data will be downloaded for cleaning and analysis.

EMA data will be collected using a wrist-worn PRO-Diary or by distributing surveys via text message through Qualtrics. EMA ratings at wake and bedtime will be initiated by the participant upon waking (not necessarily when they get out of bed) and at bedtime (“lights out” or the time they intend to go to sleep, not necessarily the

Figure 5 Pro-Diary- a wrist accelerometer

time they get into bed). An audible alert (beep) or vibration will alert participants to enter midday ratings; the PRO-Diary will be programmed to deliver the alert at a random time each day between 11:00AM and 3:00PM. The PRO-Diary will display a reminder message to complete bedtime ratings at 8:00PM each day.

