8.1 Criteria for randomization

Randomization will occur at T2 and T3 study visits. Participants with minimal or modest improvement in pain after the PainGuide run-in (PGIC \geq 2) will be randomized. Participants who have a robust improvement in their pain (PGIC<2) will not be randomized to treatment. These non-randomized participants will still complete the remaining study visits and mini-assessments. In order to assign equal numbers of participants to each of the 4 study interventions, randomization probabilities will account for the fact that certain participants, e.g. because of a contraindication, may be eligible for only 3 of the 4 treatments.

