8.2 Randomization method

We will perform randomization using a randomization software or a randomization list created by a statistician to assign participants to a treatment in an unbiased manner. A biostatistician will develop the randomization plan and will create the un-blinded randomization list to be uploaded to the software. This will enable study personnel to obtain treatment allocations and will provide functionality to manage the treatment allocation process. Furthermore, this enables study team members to maintain identifying information from participants. Study staff are not blinded to group assignment. The data analytic team are will get a coded data set and will be able to see interventions assigned to each coded participant. The data analytic team are not part of the clinical research staff and only provide data analysis. The randomization software will also track study treatment-allocation progress and provide documentation of the treatment assignment.

9 Intervention Procedures

After completing the PainGuide run-in period, participants will be assessed using either the light or light plus deep phenotyping assessment battery and those who minimal or modest improvement in their pain (PGIC \geq 2) will be randomized to one of four 8-week treatments. The treatments will be: a) MBSR, b) PT and exercise, c) acupressure self-management, and d) duloxetine. Following the first 8-week treatment period, individuals will be assessed again using either the light or light plus deep phenotyping battery and those who minimal or modest improvement in their pain (PGIC \geq 2) will be re-randomized to receive one of the treatments they did not receive in the first treatment period.

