### **5.5 Randomization and Blinding**

Blocked randomization will be used for the randomization schedule. Block size will be randomized between 4 and 8 and the ordering of treatment assignments within a block will be random.

Randomization will be performed without stratification. Study recruitment will continue until 408 patients have been randomized into a treatment group at study phase T2. We expect that it will be necessary to recruit approximately 500 patients into the study in order to achieve the target of 408 SMART participants. Based on our previous studies , we expect that approximately 15-20% of patients recruited at study phase T1 will not enter the SMART at study phase 2 due to either response to the PainGuide self-management intervention or withdrawal from the study.

We will perform randomization using a randomization software or a randomization list created by a statistician to assign participants to a treatment in an unbiased manner. A biostatistician will develop the randomization plan and will create the un-blinded randomization list to be uploaded to the software. This will enable study personnel to obtain treatment allocations and will provide functionality to manage the treatment allocation process. Furthermore, this enables study team members to maintain identifying information from participants. The randomization software will also track study treatment-allocation progress and provide documentation of the treatment assignment.

Randomization at T3 will be done similar to the one at T2.

Due to the nature of the study and its interventions, neither patients nor study staff will be blinded

to patients' treatment assignments.

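### The documents contradict themselves on whether deep phenotyping precedes allocation; if Protocol Section 10 is followed, most deep moderators are measured after an open-label assignment

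*Protocol*

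**What the plan says.** Protocol Section 10 (Deep Phenotyping Visits) makes deep phenotyping a voluntary extra: "A subset of study participants (n=160) be offered optional deep phenotyping". It is a separate appointment at a different centre from the T2 visit, and its timing is given as: "There will be two visits that take place after T2-before Treatment 1 and after T3-before Treatment 2".

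Protocol 8.1 states: "Randomization will occur at T2 and T3 study visits". SAP 5.5 states: "Due to the nature of the study and its interventions, neither patients nor study staff will be blinded" to treatment assignment. Protocol 9.4 shows that the arm is acted on at the same visit: participants randomised "to the duloxetine arm will review the dosing schedule for the medication and safety information for the medication at the pre-intervention visit", with the start set 7 days after it.

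Protocol Section 9 (Intervention Procedures) has the other order: after the run-in, "participants will be assessed using either the light or light plus deep phenotyping assessment battery and those who minimal or modest improvement" are then randomised. Protocol 3.1 and SAP 5.1 and 5.3 follow the same sequence, with deep assessment first and randomisation second.

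The schedule in SAP Table 1 puts T2 and Deep Visit 1 both in week 6 and Intervention 1 in weeks 7-14. SAP 5.6 allows ±2 weeks around T2-T5. Neither orders T2, allocation and the deep visit within that interval.

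**The concern.** SAP 9.1.2 tests whether deep measures modify the effect of treatment, using a treatment-by-moderator interaction of nearly the same form as the light analysis. That reading is secure when the moderator, and membership of the analysed subset, are fixed before allocation.

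If Deep Visit 1 follows a disclosed allocation, two routes open:

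- **Measurement.** Many QST measures are pain or unpleasantness ratings, or thresholds that the patient reports. A patient who knows the arm may rate differently according to hope or disappointment. The schedule includes preference and expectancy questionnaires, so the study team already treats these as relevant.
- **Attendance.** The visit is optional, and no section says that deep consent is obtained before the arm is disclosed. Patients could accept or decline because of their arm, which would affect every measure taken at the visit, laboratory assays included.

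Deep Visit 2 has the same ambiguity relative to the T3 re-randomisation. It supplies the post-treatment values for the exploratory paired comparisons (Protocol 10.2.1 and 18.2.2). If the deep model follows SAP 9.1.1, it also supplies the time-3 moderators.

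SAP 7.5 plans no multiplicity control, so a spurious interaction would face no such filter. Once the data are collected, the order cannot be repaired.

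**Working it through.** **1. The order, section by section**

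| Source | Order implied |
|---|---|
| Protocol 10 with Protocol 8.1 | allocation, then deep visit |
| Protocol 9.4, SAP 5.5 | arm known at T2/T3; nobody blinded |
| SAP 6; SAP 5.6 with 5.4.1 | deep patients drawn from those randomised; fits allocation first but does not require it |
| Protocol 3.1, Protocol 9, SAP 5.1, SAP 5.3 | deep visit, then allocation |
| SAP Table 1 | same week, no order |

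No section requires the deep visit to be finished before disclosure.

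**2. How many measures are exposed**

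SAP Table 3 (repeated as Table 5) has 15 rows: 7 fMRI, 2 QST, 1 MRS, 2 blood, 2 autonomic and 1 actigraphy. The first four groups make 7 + 2 + 1 + 2 = 12, and the autonomic rows bring this to 14. One of the 14, vagal tone, is labelled a mediator. The fifteenth row is baseline activity. Protocol 6.8 has the PRO-Diary worn "at baseline (sent home with watch following baseline visit) and T2-T5 to assess physical activity", so a pre-allocation T1 week exists. Protocol 18.1.2 attributes this measure to a different wrist device that the schedule does not list.

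**3. The plan's own power figure**

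The Protocol gives 81% power for r = 0.43 with n = 40 per treatment, two-sided 5%. By Fisher z, power = Φ(atanh(r)·√(n−3) − 1.96). This gives 0.4599 × 6.083 − 1.96 = 0.837, so 79.9%; with the usual bias term it is 80.8%. The figure reproduces. The SAP's 80% at r = 0.42 gives 77.7%, 78.7% with the bias term, or 81.4% by noncentral t, and also reproduces. These figures are for a within-arm correlation and do not speak to visit order.

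**4. Which distortions bias the interaction**

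Simulation: 4 arms of 40, true interaction zero, 4,000 runs, SAP rejection rule |W| ≥ 2. All effect sizes are assumptions chosen for illustration.

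| Scenario, affecting one arm | Mean interaction estimate | Rejection |
|---|---|---|
| No distortion | 0.00 | 4.9% |
| Uniform shift of 0.5 SD | 0.00 | 4.4% |
| Shift of 0.5 SD per SD of a factor correlated 0.5 with outcome | −0.20 | 21% |
| Attendance depending on moderator and outcome (about half attend) | +0.15 | 8% |

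Monte Carlo error near 5% is √(0.05 × 0.95/4000) ≈ 0.3 percentage points.

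The second row follows directly: adding a constant within an arm leaves the within-arm slope unchanged, and the treatment main effect absorbs it. The third can be checked by hand. With M = Z + 0.5U and Y = −0.5U + error, the slope is (0.5 × −0.5)/(1 + 0.25) = −0.25/1.25 = −0.20, against 0 in the other arms.

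The simulation has no covariates. The SAP model adjusts for T2 pain interference, sex, age, BMI, race and education, but not for expectancy, so only prognosis not captured by those covariates would act in this way.

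**5. Why PGIC should come before the deep visit**

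If 160 people were tested before eligibility is known and the Protocol's 10-20% run-in loss applied in full (an upper range), 160 × 0.9 = 144 to 160 × 0.8 = 128 would remain, or 36 to 32 per arm. Fisher-z power at r = 0.43 would then be 75% to 70%. Restricting the visit to those with PGIC≥2 at T2 avoids losing tested run-in responders.

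**The case against.** Four sections, two of them in the SAP that governs this analysis, already put the deep assessment first. A reader of Protocol 10 and 8.1 alone might infer that every deep moderator is settled as a post-randomisation measure. The documents do not support that: they contradict themselves, and baseline activity can come from the T1 week.

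A reader might also infer that any effect of knowing the arm invalidates the tests. It does not, because a uniform shift by arm drops out. Scripted instructions, familiarisation and computer-controlled pressure (Protocol 10.1) limit the tester's influence. Blood and MRS values are not ratings, so they are exposed mainly through selective attendance. The date of deep consent is simply not stated, so selection after disclosure is possible but not shown. The pre/post analyses that use Deep Visit 2 are labelled exploratory.

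Finally, reordering is more than wording. Acupressure teaching (Protocol 9.3) takes place at the clinic visit, and the duloxetine steps (Protocol 9.4) are tied to T2/T3, while deep visits are held elsewhere.

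All of this stands and narrows the point. It does not remove it: a site that follows Section 10 and Section 8.1 as written would test after disclosure, and nothing protects ratings or attendance from that.

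**Conclusion.** This is an unresolved contradiction with a risk of bias if Protocol Section 10 is the version followed. In that case 14 of the 15 rows in SAP Table 3 are measured after an open-label allocation, for up to 160 participants, and Deep Visit 2 has the same problem for those re-randomised at T3.

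Bias in the interaction tests needs a shift or an attendance pattern that varies with prognosis, for example through treatment expectancy. The 21% and 8% rejection rates show that such bias can matter at this sample size. They rest on assumed effects and do not estimate what would happen here.

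A reader might want to express the harm as lost power, by adding expectancy variance to each moderator. The documents give no such variance, and that calculation describes independent noise weakening a correlation, which is a different problem from arm-dependent bias in an interaction.

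The exposure is confined to Aim 3. The order should be settled before further deep visits take place.

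**What to change.** Amend Protocol 10 and 8.1 to match Protocol 3.1 and 9 and SAP 5.1 and 5.3, and state the same order in the schedule:

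- Obtain deep consent and fix membership of the deep subset before allocation.
- At T2, establish PGIC. For consented deep participants with PGIC≥2, complete Deep Visit 1 before the allocation is generated and disclosed. At T3, do the same with Deep Visit 2 before re-randomisation.
- Name the T1 actigraphy week as baseline activity.
- Record the dates of disclosure and of each deep visit, and report deep attendance by arm.
- For anyone tested after disclosure, add a sensitivity analysis by actual order.

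**Cost.** About 160 participants learn their arm later, within the existing pre-treatment interval. Their allocation step then differs in timing from that of light-only participants. The arm-specific steps that Protocol 9.3 and 9.4 tie to the clinic or T2/T3 visit must be reconciled with the later disclosure, which may need one further contact at each stage. No new test is added, and the deep sample need not be enlarged for run-in responders, because PGIC is known first.
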